6.6.2.2 Dose modification and toxicity management of infusion reactions related to pembrolizumab

Pembrolizumab may cause severe or life-threatening infusion reactions including severe hypersensitivity or anaphylaxis. Signs and symptoms usually develop during or shortly after drug infusion and generally resolve completely within 24 hours of completion of infusion. Dose modification and toxicity management guidelines on pembrolizumab associated infusion reactions are provided in [Table 10].

Table 10 Pembrolizumab Infusion Reaction Dose Modification and Treatment Guidelines

NCI-CTCAE Grade	Treatment	Premedication at Subsequent Dosing
Grade 1 Mild reaction; infusion interruption not indicated; intervention not indicated	
 Increase monitoring of vital signs as medically indicated until the subject is deemed medically stable in the opinion of the investigator. 	None
Grade 2 Requires therapy or infusion interruption but responds promptly to symptomatic treatment (e.g., antihistamines, NSAIDs, narcotics, IV fluids); prophylactic medications indicated for ≤ 24 hrs	
 Stop Infusion. Additional appropriate medical therapy may include but is not limited to: 
 IV fluids antihistamines NSAIDs acetaminophen narcotics Increase monitoring of vital signs as medically indicated until the subject is deemed medically stable in the opinion of the investigator. If symptoms resolve within 1 hour of stopping drug infusion, the infusion may be restarted at 50% of the original infusion rate (e.g. from 100 mL/hr to 50 mL/hr). Otherwise, dosing will be held until symptoms resolve, and the subject should be premedicated for the next scheduled dose. 
Subjects who develop grade 2 toxicity despite adequate premedication should be permanently discontinued from further study drug treatment.
	Subject may be premedicated 1.5 hrs (± 30 minutes) prior to infusion of study intervention with: diphenhydramine 50 mg po (or equivalent dose of antihistamine), acetaminophen 500-1000 mg po (or equivalent dose of analgesic).


Grades 3 or 4
 
Grade 3: Prolonged (i.e., not rapidly responsive to symptomatic medication and/or brief interruption of infusion); recurrence of symptoms following initial improvement; hospitalization indicated for other clinical sequelae (e.g., renal impairment, pulmonary infiltrates)
 
Grade 4: Life-threatening; pressor or ventilator support indicated
	
 • Stop Infusion. • Additional appropriate medical therapy may include but is not limited to: 
 ○ Epinephrine** ○ IV fluids ○ antihistamines ○ NSAIDs ○ acetaminophen ○ narcotics ○ oxygen ○ pressors ○ corticosteroids • Increase monitoring of vital signs as medically indicated until the subject is deemed medically stable in the opinion of the investigator. • Hospitalization may be indicated. 
**In cases of anaphylaxis, epinephrine should be used immediately.
 
Subject is permanently discontinued from further study drug treatment.
	
No subsequent dosing

IV: intravenous; NSAID: nonsteroidal anti-inflammatory drug; po: by mouth
 
Appropriate resuscitation equipment should be available at the bedside and a physician readily available during the period of drug administration. For further information, please refer to the National Cancer Institute Common Terminology Criteria for Adverse Events v5.0 (NCI-CTCAE) at http://ctep.cancer.gov/.
		

6.6.2.3 Other allowed dose interruption for pembrolizumab

If the medical monitor and site investigator determine that a dose interruption for pembrolizumab is needed, an interruption of all day 1 dose of enfortumab vedotin must also occur and may last for up to 3 weeks (1 cycle). Pembrolizumab may be interrupted for situations other than treatment-related AEs such as medical or surgical events and/or unforeseen circumstances not related to study therapy. However, pembrolizumab is to be restarted within 3 weeks of the originally scheduled dose and within 42 days of the previously administered dose, unless otherwise discussed with the sponsor. The reason for interruption is to be documented in the subject's eCRF.

6.7 Overlapping Adverse Reactions

Some AEs, including rash or skin reactions, may represent overlapping toxicities for enfortumab vedotin and pembrolizumab, and attribution of skin reactions to an individual study treatment may be difficult. The management actions (i.e., to withhold or discontinue study treatment) for skin reactions should apply to both enfortumab vedotin and pembrolizumab, and the investigator should follow the most conservative dose modification guidelines as described in [Section 6.6]. However, for grade 2 skin reactions that are stable (not worsening and in the absence of fever) with supportive measures and not limiting the subject's activities of daily living, continued dosing of enfortumab vedotin may be considered following consultation with the sponsor.

6.8 Criteria for Continuation of Treatment

Options to provide enfortumab vedotin and/or pembrolizumab to subjects who are continuing to receive treatment and are benefiting will be determined at the time of cohort closure or study closure. The continued access to pembrolizumab will end when a criterion for discontinuation is met or 35 doses of pembrolizumab have been administered.

6.9 Treatment of Overdose

In the event of an overdose of $> 10\%$ of enfortumab vedotin, the site should notify the sponsor as soon as they are aware of the overdose. The subject should be closely monitored for adverse reactions. Supportive care per institutional standards should be administered.

For this study, an overdose of pembrolizumab will be defined as any dose of 1000 mg or greater. No specific information is available on the treatment of overdose of pembrolizumab. In the event of overdose, the subject should be observed closely for signs of toxicity. Appropriate supportive treatment should be provided if clinically indicated.

7 STUDY PROCEDURES AND ASSESSMENTS

7.1 Efficacy Assessments

Radiographic and response assessments will be performed according to the Schedules of Assessments [Table 1] and [Table 2]. For all cohorts, disease response and progression will be evaluated using RECIST Version 1.1 (see [Appendix 12.9, RECIST Version 1.1]). In addition, for cohort 9, disease assessments will also be evaluated using iRECIST (see Section 7.1.3).

7.1.1 Imaging for Disease Assessment (Computed Tomography/Magnetic Resonance Imaging)

For cohorts 1 to 8, imaging/disease assessment will be performed at screening/baseline and every 8 weeks ($56 \text{ days} \pm 7 \text{ days}$) from the first dose of study treatment throughout the study until the subject has radiologically-confirmed disease progression, initiates a new subsequent anticancer therapy, dies, withdraws consent, is lost to follow-up or the study closes, whichever occurs first. Baseline imaging performed prior to informed consent as standard of care may be used as long as it is performed within 28 days prior to the first dose of study treatment.

Disease response and progression will be assessed by the investigator. If disease response is assessed as CR or PR by investigator, a confirmatory imaging scan is required 4 weeks ($28 \text{ days} + 7 \text{ days}$) after the first response. After 1 year on study treatment, the frequency of disease response assessments will be reduced to every 12 weeks ($84 \text{ days} \pm 7 \text{ days}$).

In cohort 9, the first on-study imaging/disease assessment will be performed 9 weeks ($63 \text{ days} \pm 7 \text{ days}$) from the first dose of study treatment and then every 6 weeks ($42 \text{ days} \pm 7 \text{ days}$) throughout the study. After 18 months on study treatment, the frequency of disease response assessments will be reduced to every 9 weeks ($\pm 7 \text{ days}$). Baseline imaging performed prior to informed consent as part of standard of care may be used as long as it is

performed within 28 days prior to the first dose of study treatment. Tumor imaging should also be performed whenever disease progression is suspected. Objective responses will be confirmed per RECIST Version 1.1 with repeat scans at least 4 weeks (+7 days) after first documentation of response.

Imaging for cohort 9 should include the head, neck, chest and abdomen at the specified timepoints. A CT from the vertex of the head to the thoracic inlet or a brain CT is strongly preferred. Imaging of the pelvis is optional.

Treatment beyond disease progression per RECIST Version 1.1 may be considered for subjects in cohort 9 who are deriving clinical benefit. Subjects with unconfirmed progressive disease (iUPD) who are clinically stable may continue on study treatment until iCPD per iRECIST guidelines [Seymour et al, 2017] as assessed by the investigator. Confirmatory scans should be performed at the next scheduled disease assessment (6 weeks \pm 1 week).

Subjects in cohorts 1 to 8 who discontinue study treatment for reasons other than radiologically-confirmed disease progression by RECIST Version 1.1 will continue to receive imaging scans every 8 weeks (56 days \pm 7 days) until subject has radiologically-confirmed disease progression, initiates a new anticancer therapy, dies, withdraws consent, lost to follow-up, or the study closes, whichever occurs first. Tumor imaging should also be performed whenever disease progression is suspected.

Subjects in cohort 9 who discontinue study treatment for reasons other than radiographically confirmed disease progression will continue to receive response assessments, including CT scans with contrast, every 6 weeks (\pm 7 days) according to the original schedule calculated from cycle 1 day 1 up to 18 months after first dose, then every 9 weeks (\pm 7 days). Scans are to be done until the subject has radiologically confirmed disease progression per iRECIST guidelines as determined by the investigator, initiates a subsequent anticancer therapy, dies, the study closes, or the subject withdraws consent, whichever occurs first. The investigator will make treatment decisions based on site assessments of scans by iRECIST guidelines. Clinical response will be determined at each assessment per RECIST Version 1.1 or per iRECIST guidelines when applicable. Clinical response of CR, PR, SD, or PD will be determined at each assessment.

Brain scan and bone imaging will be performed according to the Schedules of Assessments for Cohorts 1-8 in [Table 1] and brain scan according for Cohort 9 [Table 2] will be repeated at response assessment time points if metastases were identified at screening/baseline, or if metastasis is known or suspected, or as clinically indicated throughout the study.

A CT scan with contrast is the preferred modality for tumor assessment. Magnetic resonance imaging is acceptable if local standard practice or if CT scans are contraindicated in a subject (e.g., subject is allergic to contrast media). All other RECIST-approved scanning methods such as x-ray are optional. The same imaging modality should be used throughout the study. Additional instructions for imaging assessments can be found in the study procedures manual.

The assessment will include tumor measurements for target lesions, nontarget lesions and any new lesions. A response assessment will be characterized for a given time point evaluation. At the end of study for each subject, the best overall response (BOR) to the study regimen will be derived. To ensure comparability, the screening and subsequent assessment of response should be performed using identical techniques. The same individual should assess images for any 1 subject for the duration of the study if possible.

The site of disease progression including target, nontarget and/or new lesions should be documented in the eCRF. Additional imaging may be performed at any time to confirm suspected progression of disease.

This study will be analyzed based on the results of local (investigator) radiological assessments. Copies of all imaging scans will also be sent to the independent review facility in a timely manner. Images at the independent review facility will be stored. Imaging scans for a cohort may be read at the independent review facility when the minimum number of responders per investigator assessment (subjects with confirmed CR and PR) to claim promising antitumor activity at stage 1 are met based on the 2-stage BOP2 design. Central images may also be read in certain circumstances as determined by the sponsor.

7.1.2 RECIST Version 1.1 Assessment

7.1.2.1 Evaluation of Target Lesions

7.1.2.1.1 Complete Response

CR is defined as disappearance of all target and nontarget lesions. Any pathological lymph nodes (whether target or nontarget) must have reduction in short axis to < 10 mm from baseline measurement.

7.1.2.1.2 Partial Response

PR is defined as at least a 30% decrease in the sum of diameters (longest for nonnodal lesions; short axis for nodal lesions) of target lesions taking as reference to the baseline sum diameters.

7.1.2.1.3 Stable Disease

SD is defined as neither sufficient decrease to qualify for PR nor sufficient increase to qualify for progressive disease taking as reference the smallest sum of diameters while on study drug.

7.1.2.1.4 Progressive Disease

PD is defined as at least a 20% increase in the sum of diameters (longest for nonnodal lesions; short axis for nodal lesions) of the target lesions, taking as reference the smallest sum on study (this includes the baseline sum if that is the smallest on study). In addition to the relative increase of 20%, the sum must also demonstrate an absolute increase of at least 5 mm. The appearance of 1 or more new lesions is also considered progression.

7.1.2.2 Evaluation of Nontarget Lesions

To achieve unequivocal progression on the basis of nontarget lesions, there must be an overall level of substantial worsening in nontarget disease such that, even in presence of SD or PR of target lesions, the overall tumor burden has increased sufficiently to merit discontinuation of therapy. A modest increase in the size of 1 or more nontarget lesions is usually not sufficient to qualify for unequivocal progression.

7.1.2.2.1 Non-complete Response/Non-progressive disease

NonCR/NonPD of nontarget lesions is defined as persistence of 1 or more nontarget lesions.

7.1.2.2.2 Progressive Disease

PD of nontarget lesions is defined as unequivocal progression of existing nontarget lesions or the appearance of 1 or more new lesions.

7.1.3 iRECIST Assessment

Response will also be assessed using iRECIST guidelines [Seymour et al, 2017] for Cohort 9. Immunotherapeutics may result in infiltration of immune cells leading to transient increase in the size in malignant lesions, or undetectable lesions becoming detectable. The criteria are identical to those of RECIST Version 1.1 in many respects but have been adapted to account for instances where an increase in tumor burden, or the appearance of new lesions, does not reflect true tumor progression.

Key differences are described below. All responses defined using iRECIST guidelines are designated with a prefix. iRECIST time point and best responses will be recorded separately.

Confirming Disease Progression

Unlike RECIST Version 1.1, the iRECIST guidelines require the confirmation of progression and uses the terms iUPD (unconfirmed immune progressive disease) and iCPD (confirmed immune progressive disease). Confirmatory scans should be performed at the next scheduled disease assessment (6 weeks \pm 1 week). iCPD is confirmed if further increase in tumor burden, compared to the last assessment, is seen as evidenced by 1 or more of the following:

- Continued increase in tumor burden (from iUPD) where RECIST Version 1.1 definitions of progression had been met (from nadir) in target, nontarget disease or new lesions
- Progression in target disease worsens with an increase of at least 5 mm in the absolute value of the sum
- Continued unequivocal progression in nontarget disease with an increase in tumor burden
- Increase in size of previously identified new lesion (s) (an increase of at least 5 mm in the absolute value of the sum of those considered to be target new lesions) or additional new lesions
- RECIST Version 1.1 criteria are met in lesions types (target and/or nontarget and/or new lesions) where progression was not previously identified, including the appearance of additional new lesions

If iUPD is not confirmed at the next assessment, then the appropriate response will be assigned (iUPD if the criteria are still met, but no worsening, or iSD [immune stable disease], iPR [immune partial response] or iCR [immune complete response] if those criteria are met compared to baseline). Please refer to the iRECIST guidelines [Seymour et al, 2017] for more details.

New Lesions

New lesions should be assessed and measured as they appear using RECIST Version 1.1 criteria (maximum of 5 lesions, no more than 2 per site, at least 10 mm in long axis or 15 mm in short axis for nodal lesions), and recorded as New Lesions-Target (NLT) and New Lesion-Non-Target (NLNT) to allow clear differentiation from baseline target and nontarget lesions.

New lesions may either meet the criteria of NLT or NLNT to drive iUPD (or iCPD). However, the measurements of target lesions should NOT be included in the sum of measures of original target lesions identified at baseline. Rather, these measurements will be collected separately in the case report form.

7.1.4 Evaluation of Time Point Response

The response status at each time point for all subjects will be reported.

7.1.5 Survival Status

After radiologically-confirmed disease progression or initiation of subsequent anticancer therapy, whichever occurs first, subjects will be contacted every 12 weeks in the long-term follow-up period for survival status until death, withdrawal of consent, lost to follow-up, or study closure, whichever occurs first. Sponsor may choose to discontinue the collection of survival status for any cohort.

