In the treatment period, starting at cycle 1, subjects in cohorts 1 to 8 will receive enfortumab vedotin on days 1, 8, and 15 every 28-day cycle until one of the treatment discontinuation

criteria are met. Subjects in cohort 9 will receive enfortumab vedotin on days 1 and 8 and pembrolizumab on day 1 of each 21-day cycle until a discontinuation criteria is met.

For cohorts 1 to 8, imaging scan and disease assessment will be performed at screening/baseline and repeated every 8 weeks (56 days \pm 7 days) from the first dose of study treatment throughout the study until the subject has radiologically-confirmed disease progression, initiates a new subsequent anticancer therapy, dies, withdraws consent, is lost to follow-up or the study closes, whichever occurs first. After 1 year on study treatment, the frequency of disease assessment will be reduced to every 12 weeks (84 days \pm 7 days).

Subjects in cohorts 1 to 8 who discontinue study treatment for reasons other than radiologically-confirmed disease progression by RECIST Version 1.1 will enter into a post treatment follow-up period and continue to receive imaging scans every 8 weeks (56 days \pm 7 days) until the subject has radiologically-confirmed disease progression, initiates a new anticancer therapy, dies, withdraws consent, is lost to follow-up or the study closes, whichever occurs first.

In cohort 9, the first on-study imaging and disease assessment will be performed 9 weeks (63 days \pm 7 days) from the first dose of study treatment and then every 6 weeks (42 days \pm 7 days) throughout the study until the subject has radiologically-confirmed disease progression (iCPD per iRECIST), initiates a new subsequent anticancer therapy, dies, withdraws consent, is lost to follow-up or the study closes, whichever occurs first. Subjects in cohort 9 with unconfirmed progressive disease per iRECIST guidelines [Seymour et al, 2017] who are clinically stable may continue on study treatment until progression is confirmed by the investigator (iCPD) at the next imaging assessment 6 weeks (\pm 7 days) after iUPD. Treatment with pembrolizumab will be discontinued once the subject has received a maximum of 35 administrations of pembrolizumab (approximately 2 years).

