Subjects in cohort 9 who discontinue study treatment (both enfortumab vedotin and pembrolizumab) for reasons other than radiologically confirmed disease progression per iRECIST will enter into a post treatment follow-up period and have physical exams, ECOG and disease assessments every 6 weeks (\pm 7 days) up to 18 months after first dose, then every 9 weeks (\pm 7 days) until the subject has radiologically confirmed disease progression per iRECIST as determined by the investigator, initiates a subsequent anticancer therapy, dies, withdraws consent, or the study closes. During study treatment, palliative radiotherapy on a nontarget lesion that is not progressing will not be considered a subsequent anticancer therapy; however, radiotherapy on any target lesion will be a subsequent anticancer therapy.

Copies of all imaging scans will also be sent to the independent review facility in a timely manner. Images at the independent review facility will be stored. Imaging scans for a cohort may be read at the independent review facility when the minimum number of responders per investigator assessment (subjects with confirmed CR and PR) to claim promising antitumor activity at stage 1 are met based on the 2-stage BOP2 design. Central images may also be read in certain circumstances as determined by the sponsor.

An end of treatment (EOT) visit will be performed within 7 days after the last dose of enfortumab vedotin or the decision to discontinue treatment, or prior to initiation of another

anticancer therapy, whichever occurs earlier. This will be followed by a 30-day safety follow-up to be completed 30 days (+ 7-day window) from the last dose of enfortumab vedotin. The 30-day follow-up assessments should be completed prior to the initiation of another anticancer therapy.

After radiologically-confirmed disease progression or initiation of subsequent anticancer therapy, whichever occurs first, subjects will be contacted every 12 weeks in the long-term follow-up period for survival status until death, withdrawal of consent, lost to follow-up or study closure, whichever occurs first. Telephone contact with the subject is sufficient in the long-term follow-up period unless any assessment must be repeated to confirm resolution of drug-related AEs.

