confirmed disease progression per iRECIST as determined by the investigator, initiates a subsequent anticancer therapy, dies, withdraws consent, or the study closes. During study treatment, palliative radiotherapy on a nontarget lesion that is not progressing will not be considered a subsequent anticancer therapy; however, radiotherapy on any target lesion will be a subsequent anticancer therapy.

Copies of all imaging scans will be sent to the independent review facility in a timely manner. Central images may be read for a cohort after the minimum number of responders (confirmed ORR) at stage 1 based on the 2-stage BOP2 design are met per investigator assessment. Central images may also be read in certain circumstances as determined by the sponsor.

An end of treatment (EOT) visit will be performed within 7 days after the last dose of enfortumab vedotin or the decision to discontinue treatment, or prior to initiation of another anticancer therapy, whichever occurs earlier. This will be followed by a 30-day safety follow-up to be completed 30 days (+ 7-day window) from the last dose of enfortumab vedotin. The 30-day follow-up assessments should be completed prior to the initiation of another anticancer therapy.

Response (CR or PR) must be confirmed with a repeat imaging scan 4 weeks (28 days + 7-day window) after first response.

After radiologically-confirmed disease progression or initiation of subsequent anticancer therapy, whichever occurs first, subjects will be contacted every 12 weeks in the long-term follow-up period for survival status until death, withdrawal of consent, lost to follow-up or study closure, whichever occurs first.

Blood samples for pharmacokinetics and antitherapeutic antibodies (ATA) will be collected at protocol-specified time points. Validated assays will be used to measure the concentrations of enfortumab vedotin and MMAE in serum or plasma and to assess ATA. Samples for exploratory biomarkers will be collected at protocol-specified time points. Enfortumab vedotin biomarker assessments will not be used for subject selection.

Details of the schedule of clinical assessments are available in the protocol.

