5.2.4 Overall Survival

OS is defined as the time from the date of first dose of study drug until the date of death due to any cause. For a subject who is not known to have died by the end of study follow-up, OS

is censored at the date of last known alive date or at the analysis cutoff date, whichever is earlier. All dates which can support a subject's survival status (i.e., lab testing date, drug administration date) will be used to derive the last known alive date. Subjects with death or last known alive date after the analysis cutoff date will be censored at the cutoff date.

OS (in months) will be calculated as:

$$[(\text{Date of death or censoring}) - (\text{Date of first dose of study drug}) + 1] / 30.4375$$

The primary analysis population for OS is FAS.

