6.4.2.3 PFS per Investigator Assessment

PFS per RECIST Version 1.1 by investigator assessment will be summarized for each cohort in the FAS. Number and percentage of subjects with an event and each event type (death, PD), censoring and each censoring type (no event, start new anti-cancer treatment before PD or death) will be summarized. PFS will be analyzed using Kaplan-Meier methodology and Kaplan-Meier plots will be provided. The median, first quartile, third quartile and the corresponding two-sided 95% CIs will be calculated. The PFS rate at months 6, 12, 24 and 36 will be summarized along with the corresponding 95% CI if applicable.

6.4.2.4 OS

OS will be summarized for each cohort in the FAS. Number of subjects with event and censoring will be summarized. OS will be analyzed using Kaplan-Meier methodology and Kaplan-Meier plots will be provided. The median, first quartile, third quartile and the corresponding two-sided 95% CIs will be calculated. The OS rate at months 6, 12, 24, 36 will be summarized along with the corresponding 95% CI if applicable.

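### If the sponsor stops survival calls in a cohort and OS is later analysed at a cutoff after the stop, censoring depends on progression and the late OS rates are overestimated

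*Protocol*

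**What the plan says.** Protocol 7.1.5 first gives the general rule: "After radiologically-confirmed disease progression or initiation of subsequent anticancer therapy, whichever occurs first, subjects will be contacted every 12 weeks". Contact ends at death, withdrawal of consent, loss to follow-up or study closure. The section then adds the option: "Sponsor may choose to discontinue the collection of survival status for any cohort". Table 1 footnote 6 and Table 2 footnote 7 carry the same two sentences. No trigger, timing, final status check or OS cutoff is attached.

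Three places give the rule without the option. Protocol 4.1 says "subjects will be contacted every 12 weeks in the long-term follow-up period for survival status until death" or one of the other end points. The synopsis has the same wording, and SAP 2.2 describes a "long-term follow-up period for survival status until death, withdrawal of consent, lost to follow-up or study closure, whichever occurs first". Protocol 8.2 does not list a stop in survival collection among the reasons for leaving the study.

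Progression-free subjects do not depend on the calls. Those still on treatment attend dosing visits. Those who stopped treatment for another reason continue scheduled scans until progression or new therapy (Protocol 4.1).

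For analysis, SAP 5.2.4 says that OS for a subject not known to have died "is censored at the date of last known alive date or at the analysis cutoff date, whichever is earlier". It takes the last known alive date from any supporting record, including laboratory and dosing dates. SAP 6.4.2.4 states: "The OS rate at months 6, 12, 24, 36 will be summarized", where applicable. SAP 6.8 places the final analysis after all subjects have left the study.

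**The concern.** Kaplan-Meier estimation needs subjects censored at a given time to have the same outlook as those still followed. Stopping the calls breaks this in one direction. Subjects who have progressed or switched therapy lose their only routine source of survival data and are censored at their last contact. Subjects who progress after the stop leave observation at about progression. The later risk set is then mainly progression-free, and its low hazard is applied to everyone.

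OS is a secondary endpoint in every cohort. At stake are the 24- and 36-month OS rates of any cohort in which the option is used.

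**Working it through.** **Is there a figure to reproduce?** No. The documents give no sample size, event count or expected rate for OS, so the size can only be illustrated.

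**Model.** Progression-free time is exponential with rate h = ln 2 / (median PFS). A share f of PFS events are deaths. Survival after progression is exponential with rate m = ln 2 / (median post-progression survival). True OS is

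S(t) = exp(−ht) + (1 − f)·h·[exp(−mt) − exp(−ht)] / (h − m).

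OS was simulated (400,000 subjects per scenario) and analysed by Kaplan-Meier under SAP 5.2.4. Vital status is complete up to the stop. After it, progressed subjects are censored at the stop, and the others are followed to progression, death or the cutoff.

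**Set A (assumptions, none from the documents).** Median PFS 4 to 7 months, median post-progression survival 7 to 9 months, f = 0.15, accrual over 12 or 18 months, progression-free subjects followed for up to 36 more months.

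True 24-month OS in the lowest scenario (PFS 4, post-progression 7): h = 0.1733, m = 0.0990, so S(24) = 0.0156 + 0.85 × 0.1733 × (0.0929 − 0.0156)/0.0743 = 0.169, or 17%. In the highest (PFS 7, post-progression 9) the same formula gives 34%.

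With a stop 6 months after the last first dose:
- 12-month accrual: estimates of 30% and 52%, that is 30 − 17 = +13 and 52 − 34 = +18 points.
- 18-month accrual: estimates of 22% and 44%, that is +5 and +10 points.

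For scale, the sampling SD with full follow-up at n = 40 is √(0.17 × 0.83/40) = 5.9 points and √(0.34 × 0.66/40) = 7.5 points.

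Varying the stop time in Set A:

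| Stop, months after last first dose | 24-month bias (points) | 36-month bias (points) |
|---|---|---|
| 6 | +5 to +18 | see Set B |
| 12 | +1 to +6 | see Set B |
| 18 | under +1 | about +1 to +9 |
| 24 | 0 | up to +3 |

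**Set B (second set of assumptions).** Five scenarios: median PFS 5.6 months with OS 12.9 and f = 0.1, 0.2 or 0.3; PFS 3.5 with OS 12.3 and f = 0.15; PFS 5.6 with OS 9.0 and f = 0.2. The values 5.6, 12.9 and 9 are those that Protocol 2.4 reports for the phase 3 urothelial study, so they are only anchors for these tumours. Accrual is 12 months and the cutoff is month 60. Stops at months 18, 24 and 30 are therefore 6, 12 and 18 months after the last first dose.

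Base case (PFS 5.6, OS 12.9, f = 0.2):

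| OS (%) at month | 12 | 24 | 36 |
|---|---|---|---|
| True | 53.3 | 21.0 | 7.4 |
| Stop at month 18 | 55.3 | 36.3 | 26.7 |
| Stop at month 24 | 53.4 | 25.9 | 19.1 |
| Stop at month 30 | 53.4 | 21.8 | 13.1 |

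Bias (estimate minus true, points) over the five scenarios:

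| Stop at month | 12-month OS | 24-month OS | 36-month OS |
|---|---|---|---|
| 18 | +0.9 to +3.4 | +8.9 to +21.5 | +11.0 to +29.2 |
| 24 | about 0 | +1.6 to +6.5 | +7.3 to +16.3 |
| 30 | about 0 | +0.1 to +0.9 | +3.6 to +7.4 |

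The two sets agree in direction and in how fast the 24-month bias fades. In Set B, where true medians are 9.0 to 12.9 months, the median moves only with the earliest stop, by 0.2 to 1.3 months. A cohort with a longer true median would be more exposed.

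**Check of the remedy.** With the base-case cutoff set at the stop date and vital status complete to that date, 12-month OS is 53.3% to 53.4% (true 53.3%), and 24-month OS with a stop at month 30 is 21.1% (true 21.0%). Later landmarks become not estimable instead of biased. With no stop, there is no bias.

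**The case against.** The strongest reply is that this is a conditional risk. The protocol says only that the sponsor may stop. A reader might infer that OS in this study is already biased, but nothing in the documents shows the option used. Two conditions are needed: a stop while subjects are alive, and an OS cutoff after the stop. This stands.

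A reader might also infer that the documents define the end of survival follow-up in two rival ways. They do not. Section 7.1.5 holds the general rule and its qualifier together, and both schedule footnotes carry it. The synopsis, Protocol 4.1 and SAP 2.2 are overview text that leaves the qualifier out. The wording needs aligning, but it is not a contradiction of substance.

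The plan also covers part of the ground. SAP 6.8 gives each cohort its own primary analysis with a data cutoff, and SAP 5.2.4 censors later deaths and alive dates at that cutoff. A stop at or after a cohort's primary cutoff leaves that analysis intact. At the last enrolling cohort's primary analysis, only non-efficacy data are added from the other cohorts. The exposure is thus chiefly the final analysis.

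Finally, OS is descriptive with no test, the landmarks are given only where applicable, and deaths within 30 days of the last dose (90 days after pembrolizumab in cohort 9) are still reported under Protocol 7.3.5. These points limit the consequence. They do not address the selective censoring, and nothing ties the OS cutoff to the stop date.

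**Conclusion.** The point holds as a conditional gap. If survival collection is stopped in a cohort with subjects alive, and OS is then analysed at a later cutoff, censoring depends on progression and late OS is overestimated.

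The stop time governs the size. In Set A the 24-month bias is about +5 to +18 points only for a stop as early as 6 months after the last first dose. It would be wrong to quote that range as the bias in general, since by 18 months it is under +1. The 36-month rate stays biased for longer, and the 12-month rate barely moves. These figures rest on assumed PFS, post-progression survival, accrual and follow-up, because the documents give no OS assumptions for these cohorts.

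A reader might extend the concern to the go/no-go decisions. Those use confirmed ORR (Protocol 9.11, SAP 6.7) and are unaffected. This is a cheap improvement, best made before OS from any stopped cohort is analysed.

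**What to change.** Add to SAP 5.2.4: if survival collection is stopped in a cohort, vital status is collected for every subject in that cohort at the stop date; that date is the OS data cutoff for the whole cohort; later deaths and alive dates are not used; and OS rates beyond the follow-up reached by then are not reported.

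The vital-status check is needed as well as the cutoff. Calls are 12 weeks apart, so without it progressed subjects are still censored at their last call, deaths since then are missed, and a small upward bias remains.

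Carry the option into the synopsis, Protocol 4.1 and SAP 2.2, or delete it from Protocol 7.1.5 and the two table footnotes.

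The cost is a short SAP addition, aligned protocol wording and one final survival contact per subject in an affected cohort. OS follow-up after the stop is given up for the few subjects still progression-free.
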